8.6.2.2 Descriptive analysis

FEV1 results (absolute values and changes from baseline) will be summarised by treatment regimen and visit on the ITT population. This descriptive analysis will also be performed based on the PP population.

A figure with adjusted mean change from baseline in FEV1 at each visit by treatment regimen derived from the linear mixed model will be provided on the ITT population. The three treatment regimens will be plotted on the same graph. This graph will also be performed based on the PP population.

Moreover, a bar chart per treatment regimen on the ITT population for the change from baseline in best FEV1 until Day 7 showing the percentage of subjects with changes within the following change from baseline categories: < -200 mL, [-200 mL, -100 mL], [-100 mL, 0], ... [200 mL, 300 mL], \geq 300 mL. The increment may be updated if not judged suitable for the range of the data obtained.

8.6.2.3 Sensitivity analyses

MMRM on PP Population:

Additionally to assess the robustness of the ITT results, a supportive MMRM analysis using the PP population will be carried out.

ANCOVA (OC):

The primary endpoint will be analysed using an ANCOVA model estimating the effect at Day 7, using OC, including treatment, severity of airflow limitation at baseline, blood eosinophils (%) value at baseline, time from start of current COPD exacerbation to first IMP dosing, presence of cardiovascular comorbidities at screening and COPD exacerbation treatment at screening as fixed effects and baseline FEV1 value as a covariate.

The ANCOVA model results will be presented with LSMEAN and standard error (SE) of each treatment regimen as well as the adjusted mean difference between treatment regimens at Day 7 and associated two-sided 95% CIs. Each pairwise treatment regimen comparison will be tested at an alpha level of 5%. Difference will be considered and confirmed between pairwise treatments if the two-sided P-value for the test for difference is below 0.05. P-values of the effects will also be presented.

ANCOVA Model and SAS code:

The SAS code used to implement ANCOVA model for FEV1 at Day 7 and 95% CIs of differences between treatments will be similar to that shown below:

```
PROC MIXED data = dataset;
  CLASS trt severity eosino time_symp cv_comorb COPD_trt;
  MODEL change_d7 = trt severity eosino time_symp cv_comorb COPD_trt baseline /
    ddfm=KenwardRoger;
  LSMEANS trt / cl;
  LSMESTIMATE trt;
    'A vs B: Overall'1 -1 0,
    'A vs C: Overall'1 0 -1,
    'B vs C: Overall'0 1 -1 / cl;
RUN;
```

Notes:

- Change_d7 represents the change from baseline to Day 7 of the variable;
- Trt represents the treatment group;
- Severity represents the severity of airflow limitation (post-bronchodilator FEV1 at baseline (pre-dose) classified into 2 groups: < 30% or ≥ 30% of predicted normal value);
- Eosino represents the blood eosinophils (%) value at baseline (classified into 2 groups: < 2% or ≥ 2%);
- Time_symp represents the time from start of current COPD exacerbation symptoms to first IMP dosin [REDACTED];

-
- Cv_comorb represents the cardiovascular comorbidities at screening (presence or absence);
 - COPD_trt represents the COPD exacerbation treatment at screening (systemic corticosteroids only, antibiotics only or both systemic corticosteroids and antibiotics);
 - Baseline represents the baseline value of the variable;
 - Treatment order [REDACTED]
 - the ‘Overall’ least squares means and contrasts will be estimated only for the change from baseline in FEV1.

MMRM on subgroup of patients enrolled in the study under protocols V4.0 and V5.0:

For patients enrolled in the study under protocols V4.0 and V5.0, the inclusion criterion 7 regarding post-bronchodilator spirometry was removed, as it was challenging in the acute exacerbation setting to conduct pre- and post- bronchodilator spirometry. Thus, all spirometry measurements were performed ‘on bronchodilator’ for patients enrolled in the study under protocols V4.0 and V5.0 (i.e. the way of measuring the primary efficacy endpoint has been changed).

Therefore, a MMRM analysis using the ITT population will be performed as a sensitivity analysis on the subgroup of patients enrolled in the study under protocols V4.0 and V5.0.

8.6.3 Analysis of secondary efficacy endpoint(s)

The analysis of secondary efficacy endpoints will be performed on the ITT and PP populations.

8.6.3.1 Comparison of FEV1 on Days 3, 10, and 14

A descriptive summary table will be presented for FEV1 absolute values and change for baseline on Days 3, 10, and 14 by treatment regimen and visit.

Change in FEV1 from baseline (pre-dose) to Day 3 will be analysed using an ANCOVA model estimating the effect at Day 3, using OC, including treatment, severity of airflow limitation at baseline, blood eosinophils (%) value at baseline, time from start of current COPD exacerbation to first IMP dosing, presence of cardiovascular comorbidities at screening and COPD exacerbation treatment at screening as fixed effects and baseline FEV1 value as a covariate.

The ANCOVA model results will be presented with LSMEAN and standard error (SE) of each treatment regimen as well as the adjusted mean difference between treatment regimens at Day 3 and associated two-sided 95% CIs. Each pairwise treatment regimen comparison will be tested at an alpha level of 5%. P-values of the effects will also be presented.

A similar ANCOVA model will be used for analysis of:

- Change in FEV1 from baseline to Day 10
- Change in FEV1 from baseline to Day 14.

Additionally, similar analyses as detailed above (descriptive summary table and ANCOVA model) will be performed for:

- Comparison of FVC on Days 3, 7, 10, and 14 (Note: ANCOVA model includes baseline FVC value as a covariate)
- Comparison of FEV1/FVC on Days 3, 7, 10, and 14 (Note: ANCOVA model includes baseline FEV1/FVC value as a covariate).

Furthermore, descriptive summary tables will be presented for the following spirometry parameters (i.e. absolute values and change for baseline on Days 3, 7, 10, and 14 by treatment regimen and visit):

- FEV1 % of predicted normal value
- FVC % of predicted normal value
- FEV1/FVC % of predicted normal value.

8.6.3.2 Normalisation of spirometry parameters over time compared with the most recent test performed within the last 12 months outside an exacerbation

The number and proportion of patients normalised for FEV1 (i.e. FEV1 returns to a value $\geq 89\%$ of the most recent FEV1 value measured within the last 12 months outside an exacerbation) at each visit will be reported by treatment regimen and Pearson's Chi-square test (or Fisher's exact test as appropriate) will be applied to compare normalisation rates at each visit between treatment regimens (two-sided test at 5% alpha level).

Moreover, a bar chart will be presented per treatment regimen for the normalisation of FEV1 at each visit showing the percentage of subjects normalised compared with the most recent test performed within the last 12 months outside an exacerbation.

A similar analysis will be used for:

- Normalisation of FEV1/FVC (i.e. FEV1/FVC returns to a value $\geq 89\%$ of the most recent FEV1/FVC value measured within the last 12 months outside an exacerbation) at each visit.

The timepoints to consider for these analyses are Days 1 to 7, Days 10 and 14, and Weeks 8, 12 and 26.

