13.4.2 Secondary Efficacy Endpoint(s)

Efficacy will be further assessed based on the following secondary endpoints:

1. Comparison of FEV1 on Days 3, 10, and 14
2. Normalisation evaluation of spirometry parameter (FEV1, FVC and FEV1/FVC) response over time (performed from Days 1 to 7, 10, 14, and at Weeks 8, 12 and 26) compared with the most recent test performed within the last 12 months outside and exacerbation (pre-study FEV1, FVC, and FEV1/FVC value)
3. Time taken to improvement of 100 mL in FEV1 compared to Baseline versus placebo
4. Comparison of AUC of FEV1 over time among groups
5. Change in RR over time (performed daily from Days 1 to 7, 10 and 14) among groups
6. Change in RR on Days 3, 7, 10 and 14 among groups
7. Time to improvement based on EXACT-PRO total score
8. Comparison of AUC of EXACT-PRO over time among groups
9. Number of COPD-related deaths during the study

10. Number of moderate/severe COPD-related exacerbations during the study
11. Time to next moderate/severe COPD exacerbation
12. Change from Baseline at each inter-visit period and over the entire period of the study in the average EXACT-PRO total score and domain scores
13. Number of times each subject required rescue therapy during the study
14. Time from hospitalisation until the subject is medically ready (COPD-related) for discharge
15. Nonlinear mixed effects PK/PD models evaluating the relationship between BCT197 exposure and efficacy/safety endpoints.

More details and the time points for collection are given in [Section 9.1.3](#) and in the Schedule of assessments ([Table 9-1](#)). A complete list of efficacy endpoints is given in [Section 11.2](#).

These secondary efficacy parameters will be assessed using the ITT population.

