13.5.3 Analysis of Secondary Endpoints

The analysis of secondary efficacy endpoints will be performed on the ITT population.

For the secondary efficacy endpoints, data will be summarised by treatment regimen and visit.

For each continuous parameter, change from Baseline will be assessed with a MMRM analysis, with treatment regimen as a factor and the Baseline value as a covariate. The adjusted mean difference between treatments will be presented along with a 95% confidence interval for the time-points of interest.

The proportion of subjects with a COPD-related death will be summarised and compared between treatment regimens using Fisher's Exact Test.

The pharmacokinetic parameters will be summarised by dose group and visit day.

A more detailed description will be presented in the SAP.

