7.2 Handling of missing data and outliers

7.2.1 Missing data analysis methods

No strategy for imputation of missing values from subjects who dropped out will be applied because the mixed model for repeated measurements analysis done for the primary endpoint is known to produce a valid analysis if the drop-out mechanism is missing at random⁵.

The analysis (and clinical database) will only include those FEV1 results assessed as being of acceptable quality for each time point.

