8.6.2.1 Primary analysis

The primary analysis of efficacy will be based on the ITT population and observed cases.

The primary analysis will compare each of the treatment regimens together using pairwise comparison tests based on a mixed model for repeated measurements (MMRM) using an unstructured covariance matrix and the Kenward-Roger adjustment for the denominator degrees of freedom. The model will use FEV1 absolute changes at Days 2, 3, 4, 5, 6 and 7, and will include treatment [REDACTED] severity of airflow limitation at baseline (post-bronchodilator FEV1 at baseline (pre-dose) <30% or ≥30% of predicted normal value), blood eosinophils (%) value at baseline (<2% or ≥2%), time from start of current COPD exacerbation to first IMP dosing (≤2 days, 3-4 days or ≥5 days), presence of cardiovascular comorbidities at screening (yes, no) and COPD exacerbation treatment at screening (systemic corticosteroids only, antibiotics only or both systemic corticosteroids and antibiotics) as fixed effects and baseline FEV1 value as covariate. In addition the baseline FEV1 value-by-visit and the treatment-by-visit interactions will be included in the model.

LSMEAN and standard error (SE) of each treatment regimen as well as the adjusted mean difference between treatment regimens and associated two-sided 95% CIs will be obtained from the MMRM model at Days 2, 3, 4, 5, 6 and 7. Each pairwise treatment regimen comparison will be tested at an alpha level of 5%. Difference will be considered and confirmed between pairwise treatments if the two-sided P-value for the test for difference is below 0.05. P-values of the effects will also be presented.

Hypotheses:

The 'superiority' null hypothesis will be:

$H_0: T2-T1 = 0$ (T2 is equivalent to T1) vs the alternative

$H_a: T2-T1 \neq 0$ (T2 is different to T1)

MMRM model and SAS code:

The SAS code used to implement linear mixed model for repeated measures for FEV1 and 95% CIs of differences between treatments will be similar to that shown below:

PROC MIXED data = dataset;

CLASS ID trt visit severity eosino time_symp cv_comorb COPD_trt;

*MODEL change = trt visit trt*visit severity eosino time_symp cv_comorb COPD_trt baseline*

*baseline*visit / ddfm=KenwardRoger;*

REPEATED visit / subject=ID type=UN;

*LSMEANS trt*visit / cl;*

LSMEANS trt / cl;

*LSMESTIMATE trt*visit*

'A vs B: Visit 2' 1 0 0 0 0 0 -1 0 0 0 0 0 0 0 0 0 0 0,

'A vs B: Visit 3' 0 1 0 0 0 0 0 -1 0 0 0 0 0 0 0 0 0 0,

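### FEV1 at Days 3, 10 and 14 is analysed by single-visit observed-case ANCOVA, an undeclared departure from the protocol's MMRM that leaves Days 10 and 14 outside the SAP's missing-data rationale

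*SAP*

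**What the plan says.** Protocol 13.4.2 lists as its first secondary endpoint "Comparison of FEV1 on Days 3, 10, and 14". For the method, protocol 13.5.3 says "For each continuous parameter, change from Baseline will be assessed with a MMRM analysis", with treatment regimen as a factor and the baseline value as covariate. It leaves further detail to the SAP.

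SAP 8.6.3.1 says "Change in FEV1 from baseline (pre-dose) to Day 3 will be analysed using an ANCOVA model estimating the effect at Day 3, using OC" (OC meaning observed cases). For Days 10 and 14 it adds "A similar ANCOVA model will be used for analysis of" those changes. The ANCOVA adjusts for baseline FEV1 and the five fixed-effect factors named in SAP 8.6.1.

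On the primary model, SAP 8.6.2.1 says "The model will use FEV1 absolute changes at Days 2, 3, 4, 5, 6 and 7". It also says that adjusted differences and their "associated two-sided 95% CIs will be obtained from the MMRM model at Days 2, 3, 4, 5, 6 and 7", so a Day 3 contrast comes from that model too.

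On missing data, SAP 7.2.1 applies no imputation for dropouts because the MMRM used for the primary endpoint "is known to produce a valid analysis if the drop-out mechanism is missing at random".

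SAP Section 9 lists three changes from the protocol: the per-protocol definition, the added per-protocol analyses, and the steroid-dose period. The switch from MMRM to ANCOVA is not among them.

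**The concern.** There are three linked problems.

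- **Undeclared change of method.** The protocol names MMRM for this endpoint, the SAP uses something else, and the section meant to record such changes is silent.
- **A missing-data rationale that does not reach these analyses.** The argument in SAP 7.2.1 belongs to a likelihood model that conditions on each patient's earlier FEV1 values. A single-visit ANCOVA at Day 10 or 14 does not use them. It is valid only if missingness is unrelated to outcome given the baseline covariates, which is a stronger assumption.
- **Two Day 3 estimates.** One comes from the primary MMRM and one from the Day 3 ANCOVA, on overlapping data, and each is tested at 5%.

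Days 10 and 14 matter for interpretation because durability is an open question. Protocol 7.1 reports that in the earlier COPD study most regimens held their FEV1 advantage for only two days after dosing, while one repeat-dose regimen held it to Day 14.

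**Working it through.** **The plan's own figure.** Protocol 13.1 and SAP Section 5 give a difference of 100 mL, SD 230 mL, two-sided alpha 0.05 and 80% power. By the normal approximation, n per arm = 2 × (1.960 + 0.842)² × 230² / 100² = 83.0, rounded up to 84. With the t distribution, power is 79.99% at 84 and 80.5% at 85, so the stated 85 is reproduced. Allowing for 5% loss, 255 / 0.95 = 268.4, or 269, against about 270. The unadjusted standard error of a pairwise difference with 85 per arm is 230 × √(2/85) = 35.3 mL.

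**Bias at Day 14.** From the documents: SD 230 mL and about 5% dropout. Assumed: true Day 14 difference 60 mL, Day 7 to Day 14 correlation 0.75, and loss after Day 7 that is more likely at low Day 7 values. Write z for the standardised Day 7 change within arm. The loss probability is p(z) = 1 / (1 + exp(−(a − z))), with a set to give the arm's missing rate. The observed-case mean in an arm then shifts by

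0.75 × 230 × E[z | observed] = 172.5 × E[z | observed].

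| Missing rate | E[z given observed] | Shift (mL) |
|---|---|---|
| 4% | 0.0380 | 6.6 |
| 5% | 0.0471 | 8.1 |
| 6% | 0.0560 | 9.7 |
| 7% | 0.0649 | 11.2 |
| 13% | 0.1160 | 20.0 |
| 19% | 0.1652 | 28.5 |

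The observed-case difference is 60 + (active shift − placebo shift):

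| Scenario (active vs placebo) | Observed-case estimate (mL) |
|---|---|
| 6% vs 4% | 63.1 |
| 4% vs 6% | 56.9 |
| 13% vs 6% | 70.4 |
| 6% vs 13% | 49.6 |
| 19% vs 7% | 77.3 |
| 7% vs 19% | 42.7 |
| 5% vs 5%, low values lost in both | 60.0 |
| 5% vs 5%, high values lost on active, low on placebo | 60 − 2 × 8.1 = 43.7 (unrounded inputs) |

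Large-sample simulation of the same set-up agrees, giving 70 and 77 to 78 mL in the two heavier active-arm scenarios. An estimate that also uses the Day 7 value, as an MMRM would, returned 59 to 60 mL.

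If one common rule governs both arms and the drug works equally at Day 7, placebo loses slightly more. At 5% overall (5.6% placebo, 4.4% active) the observed-case estimate is 58.2 mL. With a true difference of 100 mL and correlations from 0.5 to 0.85, the same rule gives 97 to 98 mL at about 5%, 94 to 96 mL at 10% and 90 to 95 mL at 20%.

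**Day 3 twice.** Two hundred trials of 90 per arm were simulated with six visits, SD 230 mL and assumed serial correlation 0.75. A six-visit generalised least squares fit was compared with a Day 3 ANCOVA on the same data. The two agree on average. The SD of their difference is about 2 mL with complete data, 7 mL with 5% missing per visit and 13 mL with 15%. The standard error of either estimate is about 32 to 38 mL.

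**The case against.** The strongest reply is that the practical effect is small. The plan expects about 5% loss, and that covers the whole 26 weeks, so loss by Day 14 may be lower. Protocol 9.3.5 keeps patients who stop study drug in follow-up. The ANCOVA already adjusts for baseline FEV1 and five factors, so it handles any missingness those explain. Protocol 13.5.1 calls all analyses exploratory, without multiplicity adjustment. All of this stands, and it limits the weight of the point. Two things work the other way: SAP 8.1.8 removes spirometry of unacceptable quality, and protocol 10.6.1 keeps ventilated patients in the study even when assessments cannot be done. The documents give no rate for either.

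Protocol 13.5.2 restricts formal FEV1 analysis to data up to Day 7. That sentence is in the primary-endpoint section. If it governs here, Days 10 and 14 should not be tested at all; it does not license ANCOVA. It does have to be reconciled with 13.5.3 and with SAP 8.6.3.1.

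On Day 3, SAP 8.6.3.1 does attach ANCOVA to the secondary endpoint, and the MMRM contrast can be read as a by-product of the primary model. That is fair. What remains is the departure from 13.5.3, and a second Day 3 result that could fall on the other side of 0.05 in a borderline case.

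Feasibility is no obstacle. The SAP uses MMRM for EXACT-PRO (8.6.3.7), CRQ in the Stabilisation Phase (8.6.4.2) and mMRC (8.6.4.5). At Day 7 it treats the observed-case ANCOVA as a sensitivity analysis only (8.6.2.3).

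**Conclusion.** The point holds as an undeclared change of method, with a missing-data rationale that does not extend to Days 10 and 14 and a duplicated Day 3 estimate. It should be corrected, but it does not threaten the primary analysis or the sample size.

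The likely bias is small: about 3 mL in either direction on a true 60 mL near the planned dropout, against a standard error of about 35 mL. It reaches roughly 10 to 18 mL only with 13% against 6% or 19% against 7% missing. These figures rest on the assumed correlation and dropout mechanism. They also take 230 mL as the SD left after covariate adjustment; a smaller residual SD shrinks them in proportion.

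A reader might infer more than the documents support:

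- **That the Day 10 and 14 effects will be inflated.** The direction depends on which arm loses more low responders. Swapping the arms gives about 50 and 43 mL, and a common rule with a working drug is mildly conservative.
- **That equal dropout removes the problem.** It does so only if selection is the same in both arms; opposed selection at 5% each gives about 44 mL.
- **That these are completer analyses.** Each visit uses everyone observed at that visit.
- **That the same protocol breach applies to FVC and FEV1/FVC.** Protocol 13.4.2 lists only their normalisation as a secondary endpoint; the change comparisons are SAP additions.

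**What to change.** 1. Take the Day 3 FEV1 comparison from the primary MMRM and name it as the reported Day 3 result.
2. Estimate Days 10 and 14 from one MMRM on Days 2 to 7, 10 and 14, with the covariates, interactions and fallback covariance structures of SAP 8.6.2.1. Leave the primary Day 7 model as it is.
3. Keep the observed-case ANCOVAs at Days 3, 10 and 14 as sensitivity analyses.
4. Extend SAP 7.2.1 to state the missing-data assumption for the secondary FEV1 analyses, and tabulate missing FEV1 by arm, visit and reason, including rejected spirometry.
5. List any departure from protocol 13.5.3 that is kept in SAP Section 9, and state there how the Day 7 restriction in protocol 13.5.2 is read for Days 10 and 14.
6. Optionally, use the same model for the SAP-added FVC and FEV1/FVC comparisons, for consistency.

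The cost is SAP wording and a small programming change. No new data are needed, and the sample size stays at 85 evaluable per regimen.
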